5.2. General Considerations

Unless otherwise noted, continuous data will be summarized with the following descriptive statistics: number of observations (n), mean, standard deviation (STD), minimum, median, and maximum. Categorical data will be summarized with frequencies (n) and percentages (%). In cases where missing data cause percentages not to sum to 100, a missing data row will be provided. Percentages will use column totals as the denominator unless otherwise indicated. For time to event variables, the Kaplan-Meier curves will be presented if the number of patients is more than 5.

All study data will be included in study data listings. Missing data will generally be treated as missing, not imputed, unless otherwise stated.

Data summaries may also be presented for TD and NTD patients separately as specified. All summaries will be descriptive. No formal hypothesis testing is planned.

5.3. Disposition of Patients

The number and percentage of patients receiving study treatment who completed the treatment period and study period along with the associated reasons for discontinuation from treatment and/or withdrawal from study will be presented.

5.4. Demographic, Baseline Characteristics, and Disease History

The following baseline and demographic characteristics will be summarized by descriptive statistics for the ITT population as well as for TD and NTD patients separately:

- Race, ethnicity, age, sex, height, weight
- Splenectomy (yes or no), iron chelation therapy (yes or no), prior β-thalassemia treatment (yes or no)
- Baseline hemoglobin for NTD patients only and baseline transfusion burden for TD patients only.
- Baseline LIC and serum ferritin
- Baseline EPO and time from diagnosis in years
- Baseline iron intake

Demographic and baseline data, medical history, and disease history data will be listed for each patient. Medical History data will be summarized using descriptive statistics.

5.5. Study Drug Exposure

Study drug exposure will be descriptively summarized for safety population and will present the duration of exposure, the number of treatment cycles, the total dose administered, the number of patients with dose delay and reduction, and the number of patients with dose increase (titration).

The duration of exposure will be calculated as (last dose date – first dose date) + 21.

The total number of cycles will be summarized by presenting the number and percentage of patients in each category.

The total dose administered is the total amount of study drug in mg a patient received during the treatment period.

Study drug administration details will be listed for each patient.

5.6. Prior and Concomitant Medication and Procedures

5.6.1. Prior and Concomitant Medication

The prior and concomitant medications are coded with WHO dictionary. The medications will be summarized for the safety population.

Medications will be assigned as prior or concomitant based on the following rules:

- If both the start and stop date exist and are before the first dose date of study drug, the medication will be counted as prior.
- If the start date is on or after the first dose date of study drug, the medication will be counted as concomitant.
- If the start date is before the first dose date of study drug and the stop date is after the first dose date of study drug or the medication is ongoing, the medication will be counted as prior and concomitant.
- If the start date is missing and the stop date is before the first dose of study drug, the medication will be counted as prior.
- If the start date is missing and the stop date is after the first dose of study drug or the medication is ongoing, the medication will be counted as concomitant.
- If the start and stop dates are missing, the medication will be counted as concomitant.

All prior and concomitant medications will be listed for each patient.

5.6.2. RBC Transfusions

The RBC transfusion records prior to and during treatment will be listed for each patient. The hemoglobin values prior to transfusion will also be listed.

5.6.3. Non-Medication Procedures

Non-medication procedures will be coded using MedDRA Version 20.0. All non-medication procedures will be listed for each patient.

5.7. Efficacy Analyses

No formal hypothesis testing is planned. All efficacy endpoint will be performed using the ITT population.

In general, the below rules apply to the derivations of efficacy endpoints which utilize hemoglobin and RBC transfusion data unless specified otherwise:

- Hemoglobin measurements within 14 days following RBC transfusion will be excluded from the efficacy analysis.
- For each patient, all efficacy endpoints will be derived based on an analysis cutoff day, defined as the last dose + 56 days or the last date from transfusion record data, whichever is earlier.

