14. History of severe allergic or anaphylactic reactions or hypersensitivity to recombinant proteins or excipients in the investigational drug.
15. Any other condition not specifically noted above which, in the judgment of the investigator, would preclude the patient from participating in the study.

Investigational product, dosage and mode of administration:

ACE-536 drug product will be provided as either a sterile liquid formulation or a lyophilized powder formulation for reconstitution with water. Each single-use vial of the liquid formulation contains 25 mg of ACE-536 in a 0.5 mL Tris-buffered saline solution (50 mg/mL). Each single-use vial of the lyophilic formulation may contain either 25 mg, 50 mg, or 75 mg ACE-536 for reconstitution with 0.5 mL, 1 mL, or 1.5 mL water, respectively, to form a citrate-buffered solution (50 mg/mL) for injection.

ACE-536 will be administered by SC injection on Day 1 of each cycle.

Criteria for Evaluation

Safety Assessments:

- All patients will be assessed for safety by monitoring AEs, clinical laboratory tests, vital signs, electrocardiogram (ECG), anti-drug antibody (ADA) testing, abdominal MRI/ultrasound and physical examination.

Efficacy Assessments:

- Patients will be assessed for erythroid response over a 62-month period following initiation of treatment. Erythroid response endpoints will be determined by monitoring hematologic laboratory values and RBC transfusions.
- Other secondary efficacy endpoints will be assessed by examining other hematology, erythropoiesis, hemolysis, iron overload, and iron metabolism parameters.
 - Erythropoiesis parameters may include serum erythropoietin (EPO) levels, reticulocytes, nucleated RBCs and soluble transferrin receptor
 - Iron overload/metabolism parameters may include serum iron, total iron binding capacity (TIBC), transferrin, soluble transferrin receptor, calculated transferrin saturation, ferritin, non-transferrin bound iron (NTBI), hepcidin, Liver iron content (LIC), and iron chelation therapy use.

PK Assessments:

- Blood samples will be drawn to evaluate PK parameters.

Exploratory Assessments:

- Biomarkers related to the TGF- β superfamily
- Self-reported quality of life measures including but not limited to the FACT-An and SF-36 questionnaires
- Extramedullary hematopoiesis (EMH) mass size by MRI
- Spleen size by MRI
- Bone mineral density (BMD) by DXA
- Leg ulcer size
- 6-minute walk test (6MWT) distance in NTD patients.

Statistical Methods

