6MWT for NTD patients ³²					(X) ³⁰			X				
Leg Ulcer Assessment ¹⁰	Collected at each visit as applicable						Cycles 24-87: Day 484 (± 5d) through 1807 (± 5d)	X				
Serum iron studies ¹¹					X			X				
Serum folate ¹²					(X) ¹²			X				
Erythropoietin levels					X			X				
Hematology ¹³	X	X	X	X	X	X		X				
Peripheral blood smear ¹⁴					X			X				
Serum chemistry ¹⁵					X			X				
Urinalysis/urine chemistry ¹⁶					X			X				
Anti-drug antibody ¹⁷					X			X ¹⁷				
PD biomarkers ¹⁹					X			X				
Hemoglobin Electrophoresis ²⁰					(X) ²⁰			X				
Pregnancy test ²¹	X	X	X	X	X	X		X				
Menstrual History ²²					X			X				
Evaluate transfusion frequency/volume ²³	X	X	X	X	X	X		X				
Administer ACE-536	X	X	X	X	X	X						
Concomitant medications and AEs ²⁴	Collected Continuously											
Malignancy and Pre-Malignancy Monitoring										X	X	

- 1 **Screening procedures:** Other than informed consent, procedures listed as part of the 28-day screening period are only applicable to patients with treatment interruption. ECHO or MUGA (only required for patients with treatment interruption) can be performed up to 56 days prior to C1D1. If performed as part of standard of care, ECHO/MUGA does not need to be repeated. Patients with treatment interruption will need to qualify per the additional inclusion criteria listed in [Section 9.3.2](#). For patients without treatment interruption, C1D1 may coincide with EOT visit of the base study A536-04. Procedures that are required to confirm eligibility for patients without treatment interruption can be performed at the base study A536-04 EOT visit and used to confirm eligibility prior to dosing on C1D1 of study A536-06.

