23 **Transfusion frequency/volume:** Transfusion history will be collected from the EOS visit in study A536-04 through the C1D1 visit of A536-06 as available; TD patients will have a “pre-transfusion hemoglobin threshold” for requiring transfusion during the study which will be determined based on transfusion history. For TD patients without treatment interruption, baseline pre-transfusion hemoglobin threshold will be the mean of all documented pre-transfusion hemoglobin values during the 12 weeks prior to C1D1 of base study A536-04 or study A536-06 (for TD patients with treatment interruption). During treatment, if the pre-transfusion hemoglobin level is increased by ≥ 1 g/dL compared to the baseline pre-transfusion hemoglobin threshold for that patient, transfusion should be delayed by a minimum of 7 days and/or the number of units transfused should be reduced by 1 or more RBC units. Patients may be transfused at the investigator’s discretion for symptoms related to anemia or other requirements (e.g., infection).

24 **Adverse events:** Patients should be monitored for AEs throughout the study. All AEs and abnormal findings that might require modification of dosing (see [Section 10.8](#)) should be reviewed prior to dosing to ensure that the patient is still eligible to receive additional doses of ACE-536.

25 **End of Treatment (EOT):** Should be performed 28 days (± 7 days) after the last dose of ACE-536. Patients who discontinue treatment early should complete the EOT visit at the time of discontinuation.

26 **Post-Treatment Follow-Up (PTFU):** Should be performed 2 months (± 7 days) after the last dose of ACE-536.

27 **Long-Term Follow-Up (LTFU):** Should be performed every 6 months (± 14 days) after the last dose of ACE-536 for 3 years after the last dose of ACE-536 to monitor for presence of malignancy and pre-malignancy, as per standard of care.

28 **End of Study (EOS):** Should be performed 3 years after the last dose of ACE-536.

29 **Cycles 6 through 17:** Procedures and visits for Cycles 6 through 9, 10 through 13, and 14 through 17 follow the same procedures and visits as scheduled for Cycles 2 through 5, with some exceptions as noted above.

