10. TREATMENT OF PATIENTS

10.1. Selection and Timing of Dose for Each Patient

Once a patient is enrolled, the appropriate dose of ACE-536 will be administered as an SC injection on Cycle 1 Day 1. Subsequent doses will be administered every 3 weeks on Day 1 of the cycle for up to 87 cycles. Patients may not exceed 87 cycles or 1825 days after first dose, whichever occurs first. The last dose of ACE-536 may not be administered after Day 1825, regardless of the number of cycles completed. Dose reductions may be required for individual patients as outlined in the Patient Dose Modifications Rules ([Section 10.8](#)). If a dose delay is required, the patient will return weekly for assessment of hematology results and AEs until the patient is eligible to receive the next dose of ACE-536. Patients will be asked to return to the clinic for two follow-up visits, occurring approximately 28 days and 56 days after their last dose of ACE-536. Dose level titration increases may also occur for individual patients as outlined in the Individual Dose Titration rules ([Section 10.9](#)). If a patient has a positive ADA result at the last visit, the patient may be asked to return for additional ADA testing every three months, until a negative result is obtained or the result is considered to be stabilized.

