1. INTRODUCTION

This statistical analysis plan (SAP) describes the statistical methods to be used for the analysis of Acceleron Protocol A536-06. This SAP should be read in conjunction with the study protocol and electronic case report form (eCRF). This version of the plan has been developed using the protocol amendment 05 dated 12 September 2017 and eCRF v7 dated 14 March 2018. Any further changes to the protocol or eCRF may necessitate updates to the SAP.

The SAP will be signed off before the study database lock. Any deviations from the SAP will be described and justified in the final clinical study report (CSR).

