- The proportion of patients who have $\geq 33\%$ reduction in RBC transfusion burden compared to pretreatment using rolling 24-week intervals
- The proportion of patients who have $\geq 50\%$ reduction in RBC transfusion burden compared to pretreatment using rolling 24-week intervals
- The proportion of patients who have $\geq 33\%$ reduction in RBC transfusion burden compared to pretreatment during weeks 37-48
- The proportion of patients who have $\geq 50\%$ reduction in RBC transfusion burden compared to pretreatment during weeks 37-48
- The proportion of patients who have no RBC transfusions ≥ 8 weeks

For each of the above defined erythroid response rates, a point estimate will be presented along with the exact 95% confidence interval based on binomial distribution.

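### SAP 5.7 does not define the second date in its efficacy cutoff; if coded as the latest transfusion, follow-up would end at a date set by the outcome

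*SAP*

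**What the plan says.** SAP 5.7 sets general rules for efficacy endpoints built on hemoglobin and RBC transfusion data. For each patient these endpoints are derived to "an analysis cutoff day, defined as the last dose + 56 days or the last date from transfusion record data, whichever is earlier". The rules hold unless an exception is stated, and SAP 5.7.2.1 to 5.7.2.3 state none. SAP 5.7.2.2 censors ongoing response at the same day.

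The second date is not defined in the SAP or the protocol. The nearest wording is SAP 5.6.2: "The RBC transfusion records prior to and during treatment will be listed for each patient". There the records are the transfusions themselves. SAP 5.12.1 leaves visit-window rules to the programming specifications, but does not mention this cutoff.

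Three other places bear on the meaning:

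- Protocol synopsis, Efficacy Assessments: "Patients will be assessed for erythroid response over a 62-month period following initiation of treatment".
- Protocol 15.2.3 lets a transfusion-burden interval fall anywhere in treatment and follow-up after Cycle 1 Day 1, with no stop at a transfusion.
- SAP 5.7.2.1 plans a transfusion-free endpoint of at least 8 weeks: "The proportion of patients who have no RBC transfusions".

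**The concern.** A programmer who takes the latest date in the transfusion dataset gets the last transfusion. Follow-up then ends because of the event being studied: the longer a patient stays transfusion-free at the end, the more time is deleted. Four things follow under that coding.

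- A transfusion-free run after the last transfusion cannot count toward the 8-week transfusion-free rate or TD response. Runs between two transfusions still can.
- A response still ongoing at the last transfusion is cut or censored there, so the censoring is tied to the outcome.
- An NTD patient whose only transfusion came before or early in treatment loses most or all on-treatment hemoglobin data.
- A patient with no transfusion record has no second date, and the SAP does not say what applies. SAP 5.1 defines base-study NTD as fewer than 11 units in 26 weeks, which includes zero, so such patients are possible.

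At stake are the TD response rates, the transfusion-free rate, response duration and the NTD hemoglobin endpoints.

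**Working it through.** **The plan's own figure.** Protocol 10.1 allows the last dose no later than Day 1825. Then 1825 + 56 = 1881 days, and 1881 / 30.4375 = 61.8 months. This reproduces the 62 months in the synopsis, so the first limb of the cutoff fits the protocol. A stop at the last transfusion does not.

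**Inputs.** Cycles are 21 days (Protocol 10.1), so the last dose at cycle c falls on Day 1 + 21(c − 1) and the first limb is T = that day + 56. Interrupted patients contribute A536-06 data only; rollover patients also contribute A536-04 data (SAP 4.1). The rollover offset is 112 days: the last A536-04 dose on Day 85 plus 28 is Day 113, which becomes A536-06 Day 1. All transfusion patterns below are assumed.

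**Follow-up lost if the cutoff is the latest transfusion, last transfusion at Day 70 (week 10).** Interrupted: (T − 70)/T. Rollover: (T − 70)/(T + 112).

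| Treated to | Last dose | T | Interrupted | Rollover |
|---|---|---|---|---|
| Cycle 17 | Day 337 | 393 | 323/393 = 82.2% | 323/505 = 64.0% |
| Cycle 35 | Day 715 | 771 | 701/771 = 90.9% | 701/883 = 79.4% |
| Cycle 53 | Day 1093 | 1149 | 1079/1149 = 93.9% | 1079/1261 = 85.6% |
| Cycle 87 | Day 1807 | 1863 | 1793/1863 = 96.2% | 1793/1975 = 90.8% |

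**Other stopping times, interrupted, treated to cycle 87.**

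- Last transfusion on Day 1448: (1863 − 1448)/1863 = 415/1863 = 22%.
- Still transfused every 21 days: the mean gap to Day 1863 is 10 days and the maximum 20, so 10/1863 = 0.5% and 20/1863 = 1.1%.

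**Rolling TD response (at least 50% reduction, 12 weeks).** Assume a baseline of 8 units per 12 weeks (2 units every 21 days). A qualifying 84-day window then holds at most 4 units.

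- *Abrupt stop.* 2 units every 21 days, the last on Days 7, 28, 49 and 70. With the cutoff at Day 70, an interrupted patient has no 84-day on-treatment window, and every window of a rollover patient holds 8 units: a non-responder. Followed to Day 1863, the first qualifying on-treatment window for the interrupted patient starts on Day 29. Duration is 1863 − 29 + 1 = 1835 days, or 262 weeks.
- *Taper first.* 2 units on Days 64, 106 and 148, and no other transfusion from Day 23 on. The window from Day 23 to Day 106 holds 4 units and ends before the literal cutoff of Day 148, so this patient is a responder under either coding. Only duration changes: from that window, 148 − 23 + 1 = 126 days against 1863 − 23 + 1 = 1841 days.

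**NTD.** An interrupted patient transfused once, on Day 60, and treated to cycle 87 has no complete 84-day on-treatment window by Day 60. To Day 1863 there are 1863 − 84 + 1 = 1780 calendar windows, before the 14-day post-transfusion exclusion.

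**Effect on a rate.** The number of TD patients is not given. If 32 are assumed with 16 true responders, the rate is 50.0% (exact 95% CI 31.9 to 68.1%). One responder lost gives 15/32 = 46.9% (29.1 to 65.3%); three lost give 13/32 = 40.6% (23.7 to 59.4%).

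**The case against.** The strongest reply is that the SAP nowhere says the latest transfusion will be used, and that its context points elsewhere. The rule also covers NTD hemoglobin endpoints, where a stop at the last transfusion makes little sense. A final transfusion-free run is what one would expect the transfusion-free endpoint to capture. The protocol looks at 62 months. SAP section 1 says the plan is to be read with the eCRF, which is not among the documents and may hold dated entries of no transfusion. If the date means the last day transfusion status was known, little is lost. This stands as far as intent goes, and it makes the harm conditional. It does not supply a definition, and the SAP's nearest wording points the other way.

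It is also fair that the endpoints are secondary and descriptive, that SAP 5.7 plans no hypothesis test, that the TD rates would tend to err against the drug, and that the per-patient listings would let a reader see the truncation. These points limit the consequence. For a patient with no record, falling back on last dose + 56 days is the natural choice, but it is not written.

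A reader might also infer that the two limbs conflict, because the schedule row "Evaluate transfusion frequency/volume" seems to end at EOT, about 28 days after the last dose, while the other limb runs to 56 days. The documents do not support that as a defect. Taking the earlier date already handles limbs of different length. The row comes from a table whose columns are unreliable as extracted. Protocol 10.1 also plans "two follow-up visits, occurring approximately 28 days and 56 days after their last dose of ACE-536", and concomitant treatments are collected throughout.

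**Conclusion.** The point holds in conditional form. The second cutoff date is undefined, and its plain reading makes follow-up depend on the outcome and conflicts with the protocol's assessment period and intervals. It should be settled before the SAP is signed.

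Three stronger inferences are tempting and not supported:

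- That the SAP prescribes truncation at the last transfusion. It does not say so; this is one coding of an undefined term.
- That everyone who stops transfusion loses most of their follow-up. The loss is 82% to 96% for an interrupted patient last transfused at week 10, but 22% at Day 1448.
- That every such patient is lost from the rolling TD rates. Only those who stop without an earlier qualifying window are, as the tapering example shows. If there are none, those rates are unaffected.

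For the fixed windows (weeks 13–24 and 37–48) the effect also depends on how a truncated window is scored, which the SAP does not say.

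The actual size cannot be computed, because the number of TD patients, their transfusion patterns and the coding are not given. Every percentage shown is an illustration under assumed profiles.

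**What to change.** In SAP 5.7, define the cutoff as the earlier of last dose + 56 days and the last date through which the patient's transfusion status is known. Status is known from a recorded transfusion, or from a visit or contact at which transfusion was evaluated, including when the answer was none. Then state three things:

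- this is not the date of the last transfusion;
- a patient with no transfusion record is followed to last dose + 56 days, or to the last status-known date if that is earlier;
- the same date applies to the NTD hemoglobin endpoints.

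The cost is one or two SAP sentences and one derived date taken from visit dates. No clinical procedure changes.

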5.7.1. Primary Efficacy Endpoint

Since the primary objective for this study is to evaluate the long-term safety and tolerability of ACE-536 in patients with β -thalassemia who were previously enrolled in study A536-04, there is no primary efficacy endpoint specified for this study.

5.7.2. Secondary Efficacy Endpoints

5.7.2.1. Erythroid Response

Erythroid response rates will be defined as below for NTD and TD patients.

For NTD patients:

- The proportion of patients with a mean increase of ≥ 1.0 g/dL from pretreatment hemoglobin during any rolling 8 weeks
- The proportion of patients with a mean increase of ≥ 1.5 g/dL from pretreatment hemoglobin during any rolling 8 weeks
- The proportion of patients with a mean increase of ≥ 1.0 g/dL from pretreatment hemoglobin during any rolling 12 weeks
- The proportion of patients with a mean increase of ≥ 1.5 g/dL from pretreatment hemoglobin during any rolling 12 weeks
- The proportion of patients with a mean increase of ≥ 1.0 g/dL from pretreatment hemoglobin during any rolling 24 weeks
- The proportion of patients with a mean increase of ≥ 1.5 g/dL from pretreatment hemoglobin during any rolling 24 weeks
- The proportion of patients with a mean increase of ≥ 1.0 g/dL from pretreatment hemoglobin during weeks 13-24
- The proportion of patients with a mean increase of ≥ 1.5 g/dL from pretreatment hemoglobin during weeks 13-24
- The proportion of patients with a mean increase of ≥ 1.0 g/dL from pretreatment hemoglobin during weeks 37-48

- The proportion of patients with a mean increase of ≥ 1.5 g/dL from pretreatment hemoglobin during weeks 37-48

For TD patients:

- The proportion of patients who have $\geq 20\%$ reduction in RBC transfusion burden compared to pretreatment using rolling 8-week intervals
- The proportion of patients who have $\geq 33\%$ reduction in RBC transfusion burden compared to pretreatment using rolling 8-week intervals
- The proportion of patients who have $\geq 50\%$ reduction in RBC transfusion burden compared to pretreatment using rolling 8-week intervals
- The proportion of patients who have $\geq 20\%$ reduction in RBC transfusion burden compared to pretreatment using rolling 12-week intervals
- The proportion of patients who have $\geq 33\%$ reduction in RBC transfusion burden compared to pretreatment using rolling 12-week intervals
- The proportion of patients who have $\geq 50\%$ reduction in RBC transfusion burden compared to pretreatment using rolling 12-week intervals
- The proportion of patients who have $\geq 33\%$ reduction in RBC transfusion burden compared to pretreatment during weeks 13-24
- The proportion of patients who have $\geq 50\%$ reduction in RBC transfusion burden compared to pretreatment during weeks 13-24
- The proportion of patients who have $\geq 33\%$ reduction in RBC transfusion burden compared to pretreatment using rolling 24-week intervals
- The proportion of patients who have $\geq 50\%$ reduction in RBC transfusion burden compared to pretreatment using rolling 24-week intervals
- The proportion of patients who have $\geq 33\%$ reduction in RBC transfusion burden compared to pretreatment during weeks 37-48
- The proportion of patients who have $\geq 50\%$ reduction in RBC transfusion burden compared to pretreatment during weeks 37-48
- The proportion of patients who have no RBC transfusions ≥ 8 weeks

For each of the above defined erythroid response rates, a point estimate will be presented along with the exact 95% confidence interval based on binomial distribution.

